7.1 Data collection methods

Quantitative research data for the quasi-experimental pre-post and mixed-method studies will be collected using a secure third-party cloud based electronic data capture (EDC) platform that meets research / ethical standards. CDSA routine individual consultation data will be extracted from MedAL-R, a software developed by Unisanté/Wavemind (Lausanne, Switzerland) to implement the clinical algorithm (ePoct+), while HMIS aggregate facility data will be extracted from the national HMIS, following MoH approval. Qualitative research data will be collected using both EDC, audio recordings, photo documentation and video recordings (in the case of method acting) and hand-written paper notes and drawings. GPS data will be collected using a mobile device.

7.1.1 Quasi-experimental pre-post study

For each participant enrolled in the quasi-experimental pre-post study, data will be captured during the pre- and post-intervention periods according to the different assessments and Case Report Forms (CRFs) described in the visit schedule displayed in **Tab. 4**. A description of the variables collected in each CRF is available in the appendix.

Health facility visits

Quantitative research assistants will use an EDC mobile application to enter the research data of enrolled participants. The quantitative research assistant will collect from the caregiver screening information, information on care seeking behaviour, transport and costs, and clinical presentation and medical history. A number of in-depth sociodemographic and household variables will also be collected either as surrogate measures of household wealth, or known to be associated with health-seeking behaviour and / or child mortality (including maternal

education). Household wealth indicators were selected from DHS and other surveys in the study countries as those which best estimate wealth index that can be directly collected from the mother / caregiver and with a reasonable time vs. reliability trade-off. Data on laboratory investigations (if performed), final diagnosis, prescribed medication, referral or follow-up advice will be extracted from clinical notes and / or facility registers. Quantitative research assistants will seek clarification from healthcare providers only in cases where these variables are not clear from the records. Personally identifiable information (PII), including participant's name and date of birth, as well as caregiver's phone number and physical address, will be collected for linking data and detecting possible duplicates and carrying out the study follow-up.

During the post-intervention period, the research data of participants enrolled in the study will be linked with their CDSA consultation data. Additional information on oxygen saturation will be collected as recorded in clinical notes and / or facility registers. Pulse oximeter device savings will be cross-checked by quantitative research assistants at the end of the consultation where possible.

Follow-up

Quantitative research assistants will conduct the phone follow-up interviews using an EDC mobile application. Personally identifiable information (PII) will be used for contacting caregivers. A window of +3 days (Day 7 to Day 10) applies to Day 7.

Data that will be collected at Day 7 follow-up will include cure status (recovery from illness as reported by the caregiver), hospitalisation and death between Day 0 and Day 7. If appropriate, name of the referral facility and duration of hospitalization will be collected to facilitate the retrospective data collection at referral hospital level.

Higher level of care visit

Data collection at this level of care will be conducted retrospectively. A quantitative research assistant using the EDC mobile application will collect data from referral facility records, registries and discharge summaries for children whose caregiver reported at Day 7 phone follow-up that they attended a government-designated referral facility between Day 0 and Day 7. This includes attendance to hospital or emergency / inpatient area of a larger primary or secondary care facility (e.g., study facilities that can admit paediatric patients). Personally identifiable information will be collected to cross-check the identity of the patients. Arrival date and time, basic clinical information on arrival and, if admitted, admission and discharge diagnosis and admission duration will be collected. If available, data on oxygen saturation at admission, oxygen administration and intensive care unit (ICU) admission and duration will also be recorded.

7.1.2 Routine data

CDSA individual consultation data

Routine individual consultation data will be recorded in the CDSA in all intervention facilities in the post-intervention period. As part of the intervention, healthcare providers will be asked to use MedAL-R during their consultations. When they do so, they will routinely enter all data necessary for the clinical management of children 0 – 59 months of age into MedAL-R. Data used within TIMCI will cover clinical presentation (including symptoms and dangers signs), medical history (including HIV and TB status if known), all physical exams and measurements relevant for clinical assessment (including pulse oximetry), and laboratory investigations. Automated recommendations from CDSA on diagnosis and child management will also be collected, as well as healthcare provider's agreement or disagreement with these recommendations and possible additional diagnoses and treatments, which will be manually entered. A description of the variables extracted from CDSA is available in the appendix.

HMIS aggregate facility data

HMIS data will include the total number of outpatient consultations – for all patients and for children 0 – 59 months of age (disaggregated by new and follow-up visit if possible) –, disease burden, and any other relevant indicators if available (such as referral rate or mortality rate), disaggregated by age and sex if routinely collected with this granularity.

7.1.3 Other mixed methods studies

Some data required for the SPA (observation and caregiver exit interview) are common with the pre-post study and will not be collected again. To reconstruct the full SPA dataset, SPA observation and caregiver exit interviews will be linked with the pre-post study as described in Section 9.4.3. The consultation observation will be conducted by a standardised clinical observer who will record information asked or provided by the healthcare provider and / or caregiver during the consultation on key aspects relating to adherence to IMCI (or national guidelines) and the use of pulse oximetry and CDSA (post intervention). The observer will not ask any questions directly of the caregiver, but at the end of the consultation will ask a limited number of questions of the healthcare provider to record diagnosis and management.

In line with the WHO guidance on Ethical Issues in Patient Safety Research, observers in Senegal and Kenya (deemed to have sufficient experience and expertise) will be advised to intervene in the consultation only in the event that they witness an error, or suspect an imminent error, during the consultation that is "highly likely to result in direct, severe or irreversible harm" and could be mitigated by their intervention. Should they intervene, the observer will record the intervention in the sick child observation protocol instrument. No information on individual performance will be shared with supervisors, or anyone else. However, in order to mitigate the ethical issues of non-intervention when poor performance has been observed, observers in Senegal and Kenya will provide a short supportive feedback to the individual providers if they agree to it at the end of the period of observation. This will be structured in line with supervision procedures of respective MOHs. Feedback provided will be recorded.

The exit interview will be performed after the consultation by a non-clinical research assistant who will record responses to questions on additional sociodemographic and clinical details and experience of care. The healthcare provider interviews will collect information from healthcare providers involved in the care of children 0 – 59 months, on qualifications, in-service training and experience related to child health and pulse oximetry and experience of the working environment. The facility assessment will focus on the basic infrastructure, staffing, services, diagnostics and medicines relevant to child health, with additional information collected on pulse oximetry, records and reporting and management. At the end of the SPA assessment at the facility, the clinical observer and research assistant will note down additional (prompted) summary observations about the use of pulse oximetry and / or CDSA in the facility.

For the process mapping and time-flow study, pre-drawn, country-specific process maps will be reviewed and modified by research assistants with informal input from facility staff and observation. Time data will be recorded using an individual follow-through (timing one child from arrival to exit) and/or area-based (waiting area timing, consultation timing, further diagnostic timing, etc.) approach. Notes based on non-participant observation will be taken by research assistants on observations within the facility (e.g. if devices are not charged, waiting rooms are crowded, the type of interactions between patients and providers, change in provision of care (e.g. new triage system introduced)) and will not include any individual patient data.

If FGDs are conducted, they will be facilitated by a moderator and have an assigned note taker (in charge of documentation). Prior to moving to the main topics of discussion, ice-breaker exercises will be used to establish trust with participants and to provide an overview of the topic for discussion (pulse oximetry and CDSA). The classical FGDs with healthcare providers (and possibly caregivers) will use clinical vignettes which will be presented and jointly discussed.

Qualitative data from IDIs and KIIs will be collected by trained qualitative research assistants using a voice recorder, in addition to paper-based notes and drawings and a tablet for quantitative data collection. Interviews will be conducted using a semi-structured guideline interview tool, with emphasis placed on building trust and using open-ended questions with probes.

Key-informant interviews with stakeholders will either be conducted in-person or via telephone/Skype/Zoom. Interviews will be scheduled and interview questions shared in advance if wished. Surveys (using an online survey tool such as Survey Monkey) for selected stakeholders will be sent out on a regular basis via email. Participants will be asked to answer the questions and upload additional documents. A single reminder will be sent in case no response was received. Documents will be requested from partners on regular basis; a desk-review will be conducted and data entered into a document matrix.

7.1.4 Cost and modelled cost-effectiveness study

Cost data collection will occur pre- and during intervention as shown in **Fig. 3**.

Definition of costs using an activity-based approach

An activity-based approach will be explored using available cost data. Specific activities in the intervention will be allocated to different cost centres. In order to provide cost estimates that will be as managerially-, policy- and programmatically-relevant as possible, the cost analysis will adopt this approach as this separate research costs from the main programme implementation costs. The focus will be on those costs that are expected to change with the introduction of pulse oximetry and CDSAs. Costs including utilities and large equipment costs will remain the same with or without the introduction of pulse oximetry and CDSAs.

To apply the activity-based approach, we will identify specific activities that are to be costed. These will be referred to as "cost centres" (See **Tab. 6**). Cost centres are a way in which the resources used to produce the intervention activities—and the costs of those resources—are grouped. Cost centres are defined in such a way that:

- ξ The sum of the cost centres is comprehensive—including all the resources used to produce each and every activity of the program—and together, the entire program, and
- ξ They are mutually exclusive—thus avoiding double counting any of the resources used to provide the program.

It is important to note that this cost methodology is not comprehensive. As described in 5.8, it does not include the indirect costs incurred by the consumer (patient) e.g. the caregiver's time or transport costs. Rather, it focuses exclusively on the provider's direct costs, whether borne by the health system or paid out of pocket by the patient's household. The cost resources for each cost centre may differ between each country according to availability of services.

Tab. 6. Activity-Based Cost Centres of the TIMCI programme

1	Training cost for staff involved in delivering the programme:
	
- Consumable costs (including where applicable stationary, and other consumables)- Personnel costs- Overhead costs (including where applicable, rent for training venue, administrative costs, per diems and transport costs, and other overheads)
2	Delivery of intervention
	
- Annualized¹ fixed/equipment costs (including pulse oximetry device and CDSA tablet costs)- Consumable costs (including medicines, diagnostic tests, and other consumables)- Personnel costs
3	Out of pocket costs
	
- Any out of pocket costs paid by patients' households to the health system to access care and prescribed treatment will be collected, including resources purchased outside the facility due to unavailability in the facility. However, care not prescribed by facility healthcare professionals will not be included.

1. Since costing needs to account for both capital and recurrent costs, annualizing capital costs (i.e. calculating the annual value of a capital item) is the easiest way of combining capital and recurrent costs meaningfully. Annualizing capital cost is based on three pieces of important information: the initial purchase price of the item, its expected useful life, and a discount rate

Sources of cost data

Personnel and procurement units of the organisations involved in the TIMCI intervention, especially through different local PATH offices and sampled facilities will be sourced for the cost data. Centrally available databases will be used to estimate personnel and consumable (including medicines and diagnostics) costs where available.

Start-up costs, which will include training and community sensitisation costs, will be collected pre facility enrolment and intervention from PATH offices. After facility enrolment, cost data will be collected from non-medical administrative personnel. All personnel costs for those involved in the pre-intervention and intervention phase will also be collected since time in supervision, time of administrative support staff is as important as that of front line staff seeing patients. Personnel time, and volumes of diagnostic tests and treatments prescribed, will be obtained from the time-flow and service provision assessment studies. Data on time required for supervision and administrative tasks such as taking patient notes will be obtained from the senior medical professional at the facility, along with grades of personnel. Salaries of personnel according to grade will be sourced from centrally available databases which would include government salary publications for health facility workers (medical and non-medical) and complemented with salary costs sourced from health facility administrative databases where needed. Costs of consumables will also be sourced centrally where available and would for instance include cost of items on the National Essential Medicine List. Referral and hospitalization costs will be sourced from interviewing senior administrative personnel at referral health facilities.

Total programme cost and cost per child will be estimated. We will collect administrative data from appropriate levels in each country depending on organization of the specific health system, and will use time-flow data, and data collected elsewhere in the project before and after the intervention.

The table below lists the broad areas of cost data collection for each cost centre and the respective data sources.

Tab. 7. Sources of cost data

Type of Cost		Identification	Measurement		Valuation	
		Categories	Costing method	Sources of data	Valuation methods	Sources of data
Recurrent (costs incurred every year e.g. staff, maintenance, fuel)	Personnel (staff)	All staff involved (field workers and managers, administrators, support staff (drivers), etc)	Percentage of time spent on different activities within TIMCI; grade of personnel	Time data collected by operational research	Gross remuneration package costs	Centrally from government databases and complemented with provider's payroll department
	Consumables	Disposable items used per child per intervention	Quantity of consumables used per child	Medical personnel at health facility	Market prices	Centrally from government databases and complemented with provider's

						procurement department
	Equipment/ Capital (incurred every few years)	Pulse oximetry devices, tablets etc	Annualised cost of items	Interview, observations, and timing	Replacement prices	Provider's financial syndicate office
	Out of pocket costs	All out of pocket costs paid by patients' households to the health system for fever management	Direct fees and charges paid by households to health systems	Cost borne by households	Financial cost	Cost data collected from health system administrative records; information from interview of senior non- medical personnel

Definitions of types of costs and data to be collected

Staff time: For each activity within the TIMCI project, the responsible staff member involved with the activity will be identified. Secondly the time involved will be ascertained from the time-flow study and quantified. Supervision costs will similarly be estimated.

Consumables: The type and quantity of medicines, diagnostic tests and consumables used for each activity will be identified. In addition, unit costs of each consumable item will be obtained (for example the cost of an oxygen cylinder) and the size of unit (the time average spent on oxygen per patient).

Equipment: All equipment used for each activity will be identified and the price for which it was purchased. For the equipment costing, the lifespan for the equipment (usually between 3 – 5 years for smaller items including electronic tablets and pulse oximetry devices) will be obtained and annualized. Annualization will follow the cost recovery methodology where item cost, life span, and a defined interest rate is used to estimate the annual cost of an item. For equipment that is shared with other activities, the time spent per consultation will be obtained as a percentage of total time spent using each equipment and used to calculate the cost associated with the intervention after annualization. For donated equipment, market price information will be sought.

Equipment inventories and training records will be used to collect retrospective costs. Time spent by staff on consultations with children 0 – 59 months of age will be collected from data obtained in the time-flow study. Time costs will then be determined by combining staff annual salaries obtained from government sources and/or payroll offices with time spent in consultations with children. Where applicable, this personnel cost will be disclosed only to the principal researcher without the identity of staff involved. Consumables used will be examined

to determine the unit cost of each consumable, while equipment will be annualized to determine their unit costs.

All capital and start-up costs will be annualised using an appropriate length of life and discount rate. Out of pocket payments to health systems borne by households will be estimated to capture all health system costs. These costs might vary across different settings since there might be flat rates in one setting and a varied fee schedule in another. Hence, the cost data collection for out of pocket payments will be country specific. The cost of hospital referrals where applicable, will also be estimated from interviews with senior healthcare professionals at the hospital level. Data will be captured and analysed in an excel workbook.

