6.2 Eligibility criteria

6.2.1 Quasi-experimental pre-post study and pilot

Facility inclusion:

- ξ Consenting government-designated healthcare facilities within the selected geographical areas of each country
- ξ Providing curative primary care services for children 0 – 59 months of age
- ξ Oxygen available or referral mechanism in place with oxygen available at a higher level facility
- ξ Electricity available (from any source with continuous or intermittent supply)

Facility exclusion:

- ξ Attending to fewer than 20 sick children per month (based on the prior 12 month average)
- ξ Already using pulse oximetry as a routine part of outpatient-based consultations of children 0 – 59 months
- ξ Selected to be part of a major child health programmatic or research intervention during the study period likely to significantly affect the primary outcome

- ξ Inaccessible to the study team (e.g. due to weather conditions or security issues) for significant parts of the year.

Individual child inclusion:

- ξ Children 0 – 59 months for whom caregivers provide consent
- ξ Consulting for an illness, or reported to be unwell when attending for a routine visit (e.g. vaccination, growth or chronic disease monitoring)

Individual child exclusion:

- ξ Children in the immediate post-natal period or first day of life
- ξ Attending for a consultation related to trauma only (including new and follow-up presentations for burns, injuries, wounds)
- ξ Admitted within an inpatient part of the facility (including neonates delivered at the facility admitted with their mother)
- ξ Enrolled in the study within the preceding 28 days at any study facility

6.2.2 **Other mixed methods studies**

Facilities for the remaining studies will be sampled from the pre-post study facilities (and pilot facilities for healthcare provider and caregiver IDIs). A stratified sample of facilities will be selected for the SPA and process mapping and time flow study, with stratification factors including location (rural/urban) and type of health facility (if applicable, regional differences and altitude may also be taken into account). Sub-samples for qualitative studies with healthcare providers and caregivers will be sampled from SPA facilities to allow for triangulation of data between studies, but may also be sampled from non-SPA facilities to avoid research fatigue or amplification of the Hawthorne effect.

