6.5 Participant timeline

6.5.1 Quasi-experimental pre-post study

The study flowchart is presented in Fig. 5. Research assistants will screen and recruit participants in the waiting area prior to consultation as outlined in Section 9.3. Following informed consent and enrolment, research assistants (RAs) will record participant name, address and contact details (including personal and alternate contacts) for Day 7 follow-up, basic sociodemographic details, reason for attendance and care-seeking. This will be collected from the caregiver before consultation, except in critical / emergency cases who will be seen immediately by the healthcare provider. The clinical consultation will be conducted by healthcare providers, who in the post-intervention phase will have been advised to use the devices as described above.

After the consultation, the RA will use extract information from the clinical records from the caregiver (child health card and / or referral note), and / or from clinic ledgers or medical records. Information will be extracted and recorded on the final diagnosis, oxygen saturation and results of laboratory investigations (if performed), prescribed medication with dosage, referral or follow-up advice and the usage of the pulse oximeter device and/or CDSA (if applicable). Research assistants will seek clarification from healthcare providers in cases where the diagnosis is not clear from the records.

Follow-up at Day 7 will be conducted by phone by an RA. If phone follow-up fails, three attempts will be made on the subsequent three days to reach the caregiver. Community mechanisms to facilitate follow-up (such as arranging a call with a community health worker) will be used, with consent, for caregivers without access to a phone. A structured questionnaire will be administered to assess the primary and secondary outcomes, including details of any government or private hospital admission. In case of non-recovery, if the child is still at home, the study team will advise the family to return to the PHC clinic for a follow-up consultation.

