6.6.2 Mixed methods studies

We will conduct the assessment in 8 – 10 study facilities, stratified by rural / urban location and facility type, at 5 time points – pre-intervention, and early and late intervention over the post-intervention period. We will also conduct the SPA in the pilot facilities to inform intervention refinement.

At each facility at each time point, observation and exit interview assessments will be conducted over 3 – 10 working days, in order to achieve a sample size of 10 – 30 children per facility. In smaller facilities with only one provider, the target will be a minimum of 10 observations and exit interviews, whereas in larger facilities, the target will be a minimum of 20 observations and exit interviews with at least 5 for any single provider. This would result in an estimated sample size of 800 – 1000 observations over the study period. Interviews will be conducted with all consenting healthcare providers responsible for the care of sick children at the study facility during the first assessment. These will only be repeated if details have changed (e.g. training updates), or for new staff not present at the first assessment. We estimate around 20 – 40 healthcare provider interviews (depending on facility size). The full facility assessment

will be done at the first visit, and only variables which change over time will be recollected at subsequent visits.

We will conduct facility-based process mapping and time-flow assessments in each of the SPA facilities. One process map (and associated notes on the care process and its rationale or deviations) will be developed per facility during baseline, which will be revisited and revised during early and late intervention phases to reflect changes over time, resulting in 3 maps per facility. Process maps will also be developed in the pilot facilities to inform intervention refinement. Each map will involve informal discussion with 2 – 4 healthcare providers in the facility, and non-participant observation over a period of one week, during which time-flow data will also be collected (for an estimated 10 – 30 children depending on facility size).

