§ **Mapping database** – This database will be used for linking data from the study databases and the identification database. Each table will be maintained confidential under strict operating procedures for the duration of the study. The mapping between databases will not be shared or accessible outside of the research institution. When all data validation and regulatory requirements have been met, the mapping database will be destroyed, so that all the study databases and CDSA consultation database are ultimately fully anonymized and independent from each other.

In addition, **qualitative study repositories** with restricted access rights will store raw (audio-recordings, notes, drawings, photos, videos, GPS coordinates and document review grids) and processed (transcribed, translated and coded) labelled qualitative material. Unless specified otherwise per country requirements in the DMP, these repositories will be hosted on a device owned and maintained by the country research partner.

A data transfer agreement will be requested from the national competent authorities for providing access to and sharing a full copy of the de-identified study databases, de-identified consultation database and de-identified qualitative material with the core team at Swiss TPH. A subset of these database will be additionally shared with UoW as needed for the cost and cost-effectiveness study. Following approval from the national competent authorities, the copies will be stored on servers hosted in Switzerland / Canada. Data ownership will remain with the country research partner. After study termination or premature termination of the study, the de-identified databases and de-identified qualitative material will be archived by the country research partner in accordance with national laws. The shared copies will be archived for 10 years by Swiss TPH and UoW, unless otherwise stipulated by the applicable legislation. Research partners will archive study data according to the applicable national regulations. After the mandatory retention period has ended, a periodic review will check if data storage is still needed for research purposes. If not, the study data will then be deleted. All repositories, databases and related software files will be backed up by the administrator in conjunction with any updates or changes.

[figure not shown]

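### The protocol draws test and treatment volumes for costing from the time-flow and SPA studies, leaving one small observed round before the intervention, and never states what role the much larger pre-post records play

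*Protocol*

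**What the plan says.** Protocol 7.1.4 (Sources of cost data) is the only place that assigns a source to these quantities: "volumes of diagnostic tests and treatments prescribed, will be obtained from the time-flow and service provision assessment studies". Section 6.6.2 plans the SPA in "8 – 10 study facilities, stratified by rural / urban location and facility type, at 5 time points", each visit lasting 3-10 working days "in order to achieve a sample size of 10 – 30 children per facility". Section 7.3.3 splits the five rounds into one before and four after the intervention.

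Other parts of the protocol describe the source differently:

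- The next paragraph of 7.1.4 says the costing will collect administrative data "and will use time-flow data, and data collected elsewhere in the project before and after the intervention". It names no dataset.
- Tab. 6 counts medicines and diagnostic tests as consumables. For consumables, Tab. 7 gives the measure as "Quantity of consumables used per child" and the data source as medical personnel at the facility.
- In the reuse column of Tab. 5, code 3.1 (costing) appears for the time-flow tool. It does not appear for any SPA tool or for the pre-post study.
- Section 7.2.1 states: "A subset of these database will be additionally shared with UoW as needed for the cost and cost-effectiveness study". Section 9.3.3 allows costing-relevant data from other studies to be supplied as summaries.

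Meanwhile, section 6.5.1 has research assistants extract laboratory results and "prescribed medication with dosage, referral or follow-up advice" for enrolled children, and 7.1.1 repeats this. SPA children must be eligible for the pre-post study and are enrolled in it at the same visit (6.2.2, 6.7).

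**The concern.** The costing concentrates on costs expected to change with the intervention. Prescribing is one of the things the intervention is meant to change: antibiotic prescription is a primary outcome. The cost per child before and after therefore depends partly on how many drugs and tests are used in each period.

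The named source is a small subset of a dataset the study already holds, and it differs from routine care in two ways. The consultations are watched, and in both countries observers offer providers feedback after the observation period (7.1.3), which could influence later rounds. The single baseline round also covers only days within a 6-8 month period, although section 6.6 itself expects seasonal variation in disease burden. If the costing team follows the sentence literally, the before side of the comparison is imprecise and may not represent usual prescribing. If it follows Tab. 7 or the looser wording, a reader cannot tell which source was planned.

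**Working it through.** **Inputs.** From 6.6.2: 8-10 SPA facilities, 10-30 children per facility per round, 5 rounds, 800-1000 observations per country. From 7.3.3: one pre and four post rounds. From 6.6.1: Kenya 17 × 690 = 11,730 and Senegal 18 × 510 = 9,180 children per period (initial estimates); antibiotic prescription 60%; ICC 0.05 for prescription. The 1% item below is an illustrative assumption; the documents give no item frequencies.

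**Reproducing the plan's figures.** With 20 children (the midpoint of 10-30), 8 × 20 × 5 = 800 and 10 × 20 × 5 = 1000, as stated. One round is therefore 160-200 children. The stated ranges allow 8 × 10 = 80 to 10 × 30 = 300. The four post rounds pool to 640-800. The protocol's detectable antibiotic reduction of 18% also reproduces, as 10.6-10.9 points from 60%, when the full design effect is applied with two-sided alpha.

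**Can time-flow enlarge the before side?** It has one baseline round in the same facilities. Section 7.1.3 describes it as recording times and care processes, not drug or test quantities. The SPA is therefore taken as the working source.

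**SE of the pre/post change, 60% item, stable facility effects.** The same facilities appear before and after, so only within-facility variance remains: 0.24 × 0.95 = 0.228. SE = √[0.228 × (1/n_pre + 1/n_post)].

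- SPA, 160 v 640: √(0.228 × 0.0078125) = 4.2 points
- SPA, 200 v 800: √(0.228 × 0.00625) = 3.8 points
- Pre-post Kenya: √(2 × 0.228/11,730) = 0.62 points
- Pre-post Senegal: √(2 × 0.228/9,180) = 0.70 points

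**The same change with the full design effect, no credit for stable facilities.** DEFF = 1 + (m − 1) × 0.05, with the two periods treated as independent.

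- SPA, one round v one (m = 20, DEFF 1.95): √(2 × 0.24 × 1.95/160) = 7.6 points; with 200, 6.8 points
- SPA, one round v four pooled (post m = 80, DEFF 4.95): √(0.24 × 1.95/160 + 0.24 × 4.95/640) = 6.9 points; with 200 v 800, 6.2 points
- Pre-post Kenya (DEFF 35.45): √(2 × 0.24 × 35.45/11,730) = 3.8 points
- Pre-post Senegal (DEFF 26.45): √(2 × 0.24 × 26.45/9,180) = 3.7 points

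The ratio is about five to seven under stable facility effects (3.8/0.70 to 4.2/0.62) and roughly two without them.

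**Uncommon items.** At 1%, the expected baseline count is 0.01 × 160 = 1.6 to 0.01 × 200 = 2.0. The chance of seeing none, ignoring clustering, is 0.99^160 = 20% to 0.99^200 = 13%. A planned pre-post period would yield about 92-117 such cases.

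**The case against.** The strongest reply is that nothing excludes the pre-post data. The paragraph after the key sentence admits other project data, 7.2.1 and 9.3.3 permit sharing, and Tab. 5 cannot settle the matter because it also omits costing for the SPA tools that 7.1.4 plainly uses. This stands. A reader might infer that the SPA is used instead of the pre-post dataset, but the documents support only that the pre-post role is unstated and the sources do not match.

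Observation is also a defensible source. Pre-post volumes come from notes and registers, and the SAP counts free-text antibiotics only where feasible. The costing aims at a most likely average scenario, with one-way sensitivity analysis (5.8, 7.3.4). This supports keeping the SPA as a check. It does not explain resting the baseline on one round.

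Four stronger readings are tempting but fail:

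- At 3% referral, only 5-6 referred children per round would inform referral costs. Section 7.1.4 takes referral and hospitalisation costs from interviews at referral facilities.
- The cost-effectiveness model would contradict the antibiotic primary outcome. Effectiveness is modelled from referral, hospitalisation, mortality and severity (6.4.3, 7.3.4); antibiotic prescribing is not an effectiveness input.
- The protocol admits an observer effect on SPA prescribing. Its wish to "avoid research fatigue or amplification of the Hawthorne effect" (6.2.2) concerns sampling for the qualitative studies, and no observer effect is quantified.
- Precision differs about eightfold. That takes one SPA round against one and gives full credit for stable facilities; pooling the post rounds or dropping the credit shrinks the gap.

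**Conclusion.** The point holds as a matter of source and representativeness, with a moderate precision cost. Four post rounds can be pooled, but the before side stays at one observed round, and that round limits the comparison.

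How large the precision loss is depends on how stable facility effects are across periods, which the documents do not state. The figures also assume 20 children per facility per round, the planning ICC of 0.05, and the initial pre-post totals. Recruitment then ran below expectation, and no revised total is given, so the pre-post advantage may be smaller than shown.

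A reader might go on to infer that total incremental consumable cost carries a very wide error. That cannot be shown. Without item frequencies and unit costs, these SEs on proportions do not convert to an SE on cost: rare cheap items would matter little, and rare costly ones could matter.

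**What to change.** In 7.1.4, name the pre-post records of all enrolled children, by period and country, as the primary source of volumes of tests and prescribed treatments. Keep the time-flow and SPA studies for staff time, for items the pre-post forms do not capture, and as a check on register-based volumes in the children common to both. Then align Tab. 5 (add costing to the reuse entry for the pre-post study, and for the SPA tools if they are used) and Tab. 7 (state when facility personnel, rather than records, supply quantities).

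The cost is protocol or costing-plan wording and a little extra data extraction. No new data collection is needed, and sharing is already permitted. The downside is reliance on registers and free text that may be incomplete, which the SPA comparison would help to gauge.
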